878 of patients discharged from hospital consented to follow up at 3 months. We would expect similar figures for this
879 study.

880

881 **5.13 Expenses**

882

883 A payment of overtime and travel expenses will be made to paramedics each time they attend one of the study training
884 sessions. The initial training session is mandatory for all paramedics who wish to take part in the study and attendance
885 at the refresher training and exit training will be strongly encouraged.

886

887 No expenses will be payable to participants because participants will not be required to make any additional visit to
888 hospital, to their GP or to any other health or welfare professional for the study.

889

890

891 **6. STATISTICAL ANALYSES**

892

893 **6.1 Plan of analysis**

894

895 The primary outcome of mRS at discharge or 30 days post OHCA (presented dichotomously as good recovery (0-3) or
896 poor recovery/death (4-6)), and other binary outcomes, will be analysed using a multilevel logistic regression model, in
897 which the data are nested within attending paramedic. Repeated mRS scores will be analysed using multilevel logistic
898 regression for repeated measures. Survival to 6 months and other time-to-event outcomes will be analysed using

AIRWAYS-2

21st December 2017

Protocol – version 6.0.

899 survival analysis methods, again allowing for clustering of patients by paramedic. Patient responses to the individual
900 EQ-5D questions will simply be described because these will be available only for survivors. Overall quality of life
901 utility scores and patient survival will be analysed jointly to assess whether the use of the i-gel supraglottic airway
902 device simultaneously improves the patient's quality of life and reduces the risk of death.

903

904 Enrolled patients who are subsequently identified as being ineligible will remain within the trial and be included in
905 analyses with the exception of a) patients who were subsequently found to have been previously enrolled in the trial; b)
906 patients who were inadvertently enrolled in the study due to being treated as a study participant by a paramedic who
907 arrives later than second at the patient's side; c) patients who are subsequently identified as being children (aged < 16
908 years); individuals aged 16 and 17 years will be included in analyses." . Analyses will be done according to the
909 principle of intention-to-treat, and reported according to the CONSORT guidelines [46, 47].

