1791 analyses on an intention to treat basis (ITT). For patients who do not wish for their previously collected data
1792 to be used, we will exclude all data collected after the point of consent (i.e. ward movements, EQ-5D and
1793 follow-up data) from any analyses.

1794 Data on all withdrawals is captured on a specific case report form (CRF), and will be tabulated by allocation
1795 of the enrolling paramedic (**Table T3**).

1796 **3.7 Analysis populations**

- 1797 • **Population 1a:** The analysis population for the primary outcome (mRS at discharge/30-days) is all
1798 patients who receive resuscitation, are attended by an A2 paramedic and meet the eligibility criteria,
1799 i.e. all trial patients. This is also the analysis population for outcome 5 (chest compression fraction),
1800 but limited to two trusts and starting partway through the trial.

- 1801
- 1802
- 1803
- **Population 1b:** The analysis population for the second component of secondary outcome 6 (ROSC on ED arrival) is all patients who receive resuscitation, are attended by an A2 paramedic, meet the eligibility criteria and were conveyed to ED.
- 1804
- 1805
- 1806
- 1807
- **Population 2:** The analysis population for secondary outcomes 1 to 4, 6 and 7 (airway management details, but only covering ROSC during advanced airway management by A2 paramedic for outcome 6) is all trial patients who received at least one advanced airway management attempt by the enrolling A2 paramedic.
- 1808
- 1809
- **Population 3:** The analysis population for secondary outcome 8 (length of initial ICU stay) is all trial patients who were admitted to ICU.
- 1810
- 1811
- 1812
- **Population 4:** The analysis population for secondary outcome 9 (length of hospital stay) is all trial patients admitted to hospital who did not refuse consent (i.e. patients who either consent to active or passive follow-up or who die prior to approach).
- 1813
- 1814
- 1815
- 1816
- 1817
- **Population 5:** The analysis population for secondary outcomes 10 and 13 (EQ-5D health scores and state scores) and secondary outcomes 11 and 12 (time to death after discharge and mRS during follow-up) is all trial patients who consent to active follow-up, survive to 30 days/hospital discharge and provide relevant data for at least one of the three time points (30 days/hospital discharge, 3 months and/or 6 months).
- 1818
- 1819
- 1820

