Was there bystander cardiopulmonary resuscitation (CPR)?	Form B (minimal dataset/CAD) Form E1 (paramedic)	1. Form E1 2. Form B
Date and time of hospital admission/emergency department (ED) admission	Form D (minimal dataset/paramedic contact) Form E1 (paramedic) Form G (hospital staff)	1. Form G 2. Form E1 3. Form D

1833

1834 **5. DERIVATIONS**

1835 **5.1 Primary outcome**

1836 To be calculated for all patients in population 1. Modified Rankin Score (0 to 6) at hospital discharge (or 30
1837 days post-OHCA if the patient is still in hospital at that time) is recorded for all patients who survive to
1838 hospital discharge (or 30 days post-OHCA). All trial patients who do not survive to hospital discharge (or 30
1839 days post-OHCA) will be assigned a score of 6 (dead). mRS will be dichotomised and analysed as good
1840 recovery (score 0 to 3) compared to bad recovery/death (score 4 to 6).

1841 Note. mRS is also collected at 3 and 6 months post-OHCA for patients who consent to active follow-up and
1842 will be used to calculate a dichotomised score as above and utilised for the secondary outcome of mRS up to
1843 6 months.

1844 **5.2 Compression Fraction**

1845 The compression fraction (expressed as a percentage) is measured by placing a credit-card-sized CPRCard
1846 device (Laerdal Medical, Stavanger, Norway) on the patient's chest during CPR to collect chest compression
1847 data. Data are downloaded from the card and interpreted using a CPRCard Laerdal Card reader ID CPR30-
1848 LA (FEIG Electronic, Germany) and a standard algorithm.

1849 **5.3 EQ-5D**

1850 To be calculated for all patients in population 5 at up to three time points: hospital discharge/30days post
1851 OHCA, 3 months post OHCA and 6 months post OHCA.

1852 A five digit 'state' score will be derived from the mobility, self-care, usual activities, pain/discomfort and
1853 anxiety/depression scores using the following:

1854 State = 10000*mobility score + 1000*self-care score + 100*usual activities score + 10*pain/discomfort score
1855 + anxiety/depression score

1856 Each state will then be assigned a single summary index score according to a standard scale. These index
1857 scores are numerical and range from -0.59 to 1.00, with a score of 1.00 denoting perfect health. If any of the
1858 five raw scores are missing, the state score and index score will be missing.

1859 The EQ-5D questionnaire visual analogue scales are also collected. Such scores range from 0 to 100 (with

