1860 higher scores denoting higher Quality of Life (QoL)).

1861 Trial patients who did not survive to 30 days/hospital discharge will be assigned EQ-5D visual analogue scale
1862 and summary index scores of zero.

1863

1864 **5.4 Other variables**

New variable	Rules
POPULATION 0 and 1:	
Age	If date of birth ≠ missing: Age= (OHCA date – Date of birth) /365.25 If date of birth = missing: Age= approximate age (see section 4) Else missing
999 call to first crew arrival time (mins)	(First crew arrival date-incident date)*24*60 + (First crew arrival time-incident time)
POPULATION 1:	
Trial patient	If was resuscitation attempted=Yes and was incident attended by AIRWAYS-2 paramedic=Yes and did patient meet eligibility criteria=Yes, then = Yes

New variable	Rules
Survival status to hospital discharge	
If was resuscitation attempted=No or was incident attended by AIRWAYS-2 paramedic=No or did patient meet eligibility criteria=No, then = No
 
Else missing
 
If admitted to ED (Form D)=No, then = Died on scene
 
If admitted to ED=Yes, and survived to ICU admission (Form G)=No, then = Died prior to ICU admission
 
If admitted to ED=Yes, and survived to ICU admission=Yes, and survived to ICU discharge (Form G)=No, then = Died prior to ICU discharge
 
If admitted to ED=Yes, and survived to ICU admission=Yes, and survived to ICU discharge (Form G)=Yes, and transferred=Yes and level of care in transferred hospital (form G2)=Level 3 and survived to ICU discharge (Form G2)= No, then = Died prior to ICU discharge
 
If admitted to ED=Yes, and survived to ICU admission=Yes, and survived to ICU discharge=Yes and ((transferred = No) or (transferred=Yes and level of care admitted to is level 2 or 1) or (transferred=Yes and level of care admitted to is level 3 and survived to ICU discharge=Yes)) and (mRS (Form H2/I2)=6 or (mRS (Form H2/I2) ≠6 & has patient died since ICU discharge (but prior to hospital discharge) (Form W2) = Yes) or survived to hospital discharge (form H3/I3)=No), then = Died prior to hospital discharge
 
If admitted to ED=Yes, and survived to ICU admission=Yes, and survived to ICU discharge=Yes and ((transferred = No) or (transferred=Yes and level of care admitted to is level 2 or 1) or (transferred=Yes and level of care admitted to is level 3 and survived to ICU discharge=Yes)) and (mRS≠6 or survived to hospital discharge=Yes, then = Survived to 30 days/hospital discharge)

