1916 intervals (95% CI). .

1917 • **Continuous outcomes** will be summarised by means and SDs in each treatment group, if distributions
1918 are approximately normal. If distributions are non-normal data will be summarised by the median and
1919 IQR or geometric mean (GM) if a logarithmic transformation provides an approximately normal
1920 distribution. Outcomes will be compared using linear regression. For untransformed data treatment
1921 comparisons will be presented as adjusted differences in means with 95% CI, and for logarithmically
1922 transformed data as adjusted ratios of GMs with 95% CI. Due to the large numbers of trial patients not
1923 expected to survive to 30 days/hospital discharge, a two-part zero-inflated modelling approach will also
1924 be considered for EQ5D visual analogue scale and summary index scores. This will comprise a) an
1925 occurrence model, a logistic regression model for the occurrence of death vs survival; b) intensity model,
1926 a log-linear model for the score, conditional on survival. If it is not possible to fit the model, then an
1927 analysis restricted to those who survive to hospital discharge will be considered.

1928 • **Time to event outcome** time to death will be summarised by the median and IQR in each intervention
1929 group. This will be compared using Cox's proportional hazards or parametric models as appropriate. The
1930 choice of model to use will depend on the distribution of the data. The intervention comparison will be
1931 presented as a hazard ratio (HR) and 95% CI if a proportional hazards model is used or time ratios (TR)
1932 and 95% CI if an accelerated failure time (AFT) model is used. Times will be censored at last contact for
1933 patients known to be alive at that time.

1934 • **Longitudinal outcomes** will be summarised for each time point. Binary and continuous outcomes will
1935 be compared using logistic and linear mixed effects methodologies respectively, with the treatment group
1936 and study design variables (see section 6.2.1) fitted as fixed effects, and patient terms as random effects.
1937 If a time x treatment interaction is not statistically significant at the 10% level an overall treatment effect
1938 will be reported. If the interaction is statistically significant the changes in treatment effect with time will
1939 be described. Different variance/covariance structures will be explored, and the structure that provides

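### The two-part EQ-5D model puts a log scale on an index that can be zero or negative, and its stated population excludes the deaths it is meant to model

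*Protocol*

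**What the plan says.** Protocol 6.1 commits the trial to a combined analysis, in which "utility scores and patient survival will be analysed jointly".

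SAP 6.2.2 (continuous outcomes) says that a two-part zero-inflated approach will also "be considered for EQ5D visual analogue scale and summary index scores". The first part is an "occurrence model, a logistic regression model for the occurrence of death vs survival". The second is "a log-linear model for the score, conditional on survival". If the model cannot be fitted, an analysis of survivors to discharge is to be considered. Table T8 lists OR and GMR as the overall effect for both the index and the visual analogue scale (VAS); the footnote to Table T7 expands GMR as geometric mean ratio.

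SAP 5.3 states that the index "scores are numerical and range from -0.59 to 1.00". Of the VAS it says: "Such scores range from 0 to 100".

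On who is analysed, SAP 3.7 says that the EQ-5D population (Population 5) "is all trial patients who consent to active follow-up, survive to 30 days/hospital discharge and provide relevant data" for at least one time point. SAP 5.3 opens by limiting the EQ-5D derivation to Population 5, but ends: "Trial patients who did not survive to 30 days/hospital discharge will be assigned EQ-5D visual analogue scale" and index scores of zero.

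**The concern.** There are two separate problems.

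**Scale.** A geometric mean ratio comes from a model of the logarithm of the score. The stated index range crosses zero, so the living patients with the worst health states may have no logarithm. A value of zero also does not identify a death uniquely, because a survivor can have an index of zero or lower.

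**Population.** The logistic part needs deaths and survivors in the same data set. Population 5 is defined by survival to 30 days or discharge, so the deaths that motivate the model are outside it.

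At stake is the joint analysis promised in Protocol 6.1. If the two-part model fails, the stated fallback compares survivors only. That conditions on an outcome that arises after randomisation and no longer addresses survival and quality of life together.

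**Working it through.** **1. Numbers of survivors and deaths.** The total of 9,070 comes from Protocol 4.7, and it reproduces. For 8% against 10%, two-sided 5% and 90% power, the two-proportion formula gives 4,301 per group, or 4,401 with continuity correction (stated: 4,400). With 9,070/1,300 = 6.98 patients per paramedic and ICC 0.005, the design effect is 1 + (6.98 - 1) × 0.005 = 1.030, and 4,400 × 1.030 is about 4,531 (stated: 4,535). The sample size is not in dispute; it is used here only for scale.

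Protocol 4.6.2 expects 9% to survive to discharge:

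- survivors: 0.09 × 9,070 = 816
- deaths: 9,070 - 816 = 8,254

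**2. The log scale against the index range.** Over the range in SAP 5.3:

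| Index | log(index) |
|---|---|
| -0.59 | undefined |
| -0.10 | undefined |
| 0 | minus infinity |
| 0.10 | -2.30 |
| 1.00 | 0 |

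Every value from -0.59 up to and including 0 is inadmissible. On the VAS (0 to 100) only 0 itself is.

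**3. How many survivors this could touch.** The second part applies to patients in active follow-up. Protocol 5.12 reports that 86% of discharged patients in the feasibility study consented to follow-up at 3 months. Taking that as a stand-in for consent to active follow-up, 0.86 × 816 = 702. The documents give no share of survivors with an index of zero or below, so it is an assumption, shown as a range:

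| Assumed share | Patients out of 702 |
|---|---|
| 1% | 7 |
| 5% | 35 |
| 10% | 70 |
| 15% | 105 |

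**4. The logistic part in Population 5.** Of the 8,254 expected deaths before discharge, Population 5 contains none. With no deaths in either arm, the odds of death are 0 in both and the odds ratio is 0/0. A trial fit on 702 records with a constant outcome stopped with a perfect-separation warning and a singular matrix.

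**5. The sections side by side.**

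| Place | Patients covered | Effect scale |
|---|---|---|
| SAP 3.7, Population 5 | consenting survivors with data | not stated |
| SAP 5.3, opening | Population 5 | not stated |
| SAP 5.3, end | non-survivors given zero | not stated |
| SAP 6.2.2, two-part model | deaths and survivors | logistic, then log-linear |
| SAP 6.2.2, longitudinal outcomes | not stated | linear mixed model for continuous outcomes |
| Table T8 | not stated | OR and GMR |

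The population entries conflict. So do the last two rows: SAP 6.2.2 classes the EQ-5D scores as longitudinal, and the mixed model it gives for continuous longitudinal outcomes does not lead to a geometric mean ratio unless the score is log-transformed.

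**The case against.** The best defence is that the two-part model is not a fixed commitment. It is only to be considered, a fallback is named, SAP 6.2.4 allows other methods when assumptions fail, and a linear mixed model, which accepts negative values, already stands in SAP 6.2.2. A reader might infer that the whole EQ-5D analysis cannot work; the documents do not support that. The defect lies in the two-part model for the index and in the template that reports it. The soft wording does not remove it, however. Table T8 offers no mean difference, the fallback gives up the joint analysis, and the SAP amendment log justifies that fallback by the high proportion of deaths, not by non-positive scores.

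The log-linear part might instead be a log link on the mean, which can tolerate some non-positive values. But SAP 6.2.2 ties ratios of geometric means to log-transformed data, and Table T8 shows that ratio.

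On the population, the intention to include deaths is plain: SAP 5.3 scores them, and 6.2.2 introduces the model because most trial patients will die. This is therefore a contradiction between sections, not a decision to leave deaths out.

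Two further inferences are tempting and also go too far. One is that the sickest survivors' values will be deleted, to the advantage of the arm that has more of them. No section says so; a failed fit or a change of method is equally possible. The other is that patients who die after discharge become missing. For EQ-5D the text is silent on them. For mRS, SAP 5.1 derives the later scores by reference to the rule that it has just set out, and post-discharge deaths are recorded.

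**Conclusion.** The point holds for the two-part model, in two parts.

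- The log-scale part and its geometric mean ratio do not suit an index that runs down to -0.59. This follows from the stated range and needs no assumption. The number affected is unknown: roughly 7 to 105 survivors, if 1% to 15% of about 702 score zero or below and the feasibility consent rate carries over. The direction of any bias depends on how those values are handled and cannot be stated from the documents. For the VAS the problem is confined to scores of exactly 0.
- The death-against-survival part cannot be estimated in Population 5 as defined, whatever the number of survivors.

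The primary outcome and the sample size are untouched. EQ-5D at discharge, 3 and 6 months are secondary outcomes that SAP 6.2.2 keeps out of the primary paper. The correction is worth making because neither the fallback nor SAP 6.2.4 delivers what Protocol 6.1 promises.

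**What to change.** - **Death part:** fit it in all trial patients with known vital status (Population 1a), and say so in SAP 3.7 and 6.2.2.
- **Index part:** fit it among survivors on the untransformed scale, with a linear or linear mixed model and a mean difference. Replace GMR by the mean difference for the index in Table T8.
- **Sections:** align SAP 3.7, 5.3 and 6.2.2, so that the zeros given to non-survivors and the population in which EQ-5D is derived agree.
- **Later deaths:** state that the same scoring (utility 0) applies at 3 and 6 months to patients recorded as dead by then.

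The cost is wording in the SAP and one template table. The data are already being collected, and no sample-size figure changes.

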Duration of ICU stay in all patients admitted to ICU from ED (hours; median, IQR)

HOSPITAL STAY

Survived to hospital discharge
Duration of hospital stay in patients who survived to discharge (days; median, IQR)
Duration of hospital stay in patients who died before discharge (hours; median, IQR)
Duration of hospital stay in all patients admitted to ED (hours; median, IQR)

2075
2076
2077
2078
2079

¹OR=Odds ratio (from logistic or, where marked *, multinomial regression), MD=mean difference, GMR=Geometric mean ratio

[figure not shown]
Table T8 Longitudinal secondary outcomes

	Randomised to intubation (n=XX)		Randomised to i-gel (n=XX)		Overall (n=XX)	
	n	%	n	%	N	%
mRS (0 to 3; good recovery)						
Discharge/30 days						
3 months						
6 months						
Treatment*time interaction						
Overall						OR
	Randomised to intubation (n=XX)		Randomised to i-gel (n=XX)		Overall (n=XX)	
	n	%	n	%	N	%
EQ5D index score (median, IQR)						
Discharge/30 days						
3 months						
6 months						
Treatment*time interaction						
Overall						OR, GMR
EQ5D visual analogue scale score (median, IQR)						
Discharge/30 days						
3 months						
6 months						

Treatment*time interaction	
Overall	OR, GMR

2080
2081
2082
2083
2084
2085
2086
2087

Figure F7 Subgroup analyses (example for one subgroup analysis: event witnessed by ambulance staff)

2088
2089

Table T9 Unexpected serious adverse events

		Received Intubation first (n=XX)		Received i-gel first (n=XX)	
		n	%	n	%
Number of patients experiencing one or more SAEs					
Number of events					
Brief description of events					
Timing of events	Pre-surgery Post-surgery but pre-discharge Post-discharge				
Maximum intensity	Mild Moderate Severe				
Reason event classified as SAE	Resulted in death Is/was life threatening Resulted in persistent or significant disability/incapacity Prolonged ongoing hospitalisation/ caused hospitalisation Other				
Relatedness to intervention	Possibly related Probably related Definitely related				

2090
2091
2092
2093

Table T10 Details of unexpected serious adverse events

Study ID=	Intervention randomised to=	Interventions received=	Patient withdrawn from study (and when)=
OHCA date=	Hospital discharge date (if applicable)=	Death date (if applicable)=	Timing of SAE= Post-intervention but pre-discharge/ Post-discharge
Brief description of event=	Location=	Maximum intensity=	Relatedness=
SAE start date/time=	SAE resolution date/time=	Event resulted in death=	Event was life threatening=

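### The log-linear survivor model and geometric mean ratio offered for EQ-5D are undefined for survivors whose index is at or below zero, which the SAP's own index range allows

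*Protocol*

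**What the plan says.** - **Aim.** Protocol 6.1 states that quality of life "utility scores and patient survival will be analysed jointly", to see whether the i-gel improves both.
- **Scale.** SAP 5.3 says that the index "scores are numerical and range from -0.59 to 1.00, with a score of 1.00 denoting perfect health". The visual analogue scale (VAS) runs from 0 to 100. Patients who die before discharge or 30 days receive VAS "and summary index scores of zero".
- **Two-part model.** Under continuous outcomes, SAP 6.2.2 says that a two-part approach will also "be considered for EQ5D visual analogue scale and summary index scores". The occurrence part is "a logistic regression model for the occurrence of death vs survival". The intensity part is "a log-linear model for the score, conditional on survival".
- **Effect measure.** The same paragraph presents logarithmically "transformed data as adjusted ratios of GMs with 95% CI". Table T8 has one overall entry each for index and VAS, and both read OR, GMR. The footnote to Table T7 gives "GMR=Geometric mean ratio".
- **Longitudinal model.** SAP 6.2.2 classes the EQ-5D index and VAS as longitudinal, and says that continuous longitudinal outcomes will be compared by linear mixed models.
- **Fallbacks.** If the two-part model cannot be fitted, an analysis of survivors to discharge will be considered. SAP 6.2.4 adds a general clause that other methods will be sought if assumptions fail.

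**The concern.** A geometric mean ratio compares means of log(score), and the log does not exist at or below zero. The patients affected are living, followed up, and in the health states that the tariff values lowest. Leaving them out selects on the outcome after randomisation, and the selection differs between arms whenever the arms differ in severe impairment. That is part of what the joint analysis of utility and survival is meant to detect. Small positive scores raise the opposite problem: they are defined, but carry very large weight on the log scale. The estimate would then depend on which side of zero a few patients fall.

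**Working it through.** **1. Domain check.** log(1.00) = 0, log(0.01) = -4.61, log(0) is minus infinity, and log(-0.10) and log(-0.59) are undefined. The non-positive part of the stated range is 0.59 / (1.00 + 0.59) = 0.59 / 1.59 = 37% of its width. This describes the scale, not the share of patients. For the VAS, the only undefined value is exactly 0.

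**2. Whether the plan handles it.** SAP 5.3, 6.2.2 and T8 give no added constant, no rescaling (such as 1 minus the index) and no rule for non-positive scores in survivors. The survivors-only fallback does not help, because the scores in question belong to survivors and no scale is named for that analysis.

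**3. How many patients.** Inputs: 9,070 patients (Protocol 4.7) and 9% surviving to discharge (Protocol 4.6.2), so 9,070 x 0.09 = 816 survivors. The share at or below zero is not in the documents and is assumed:

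| Assumed share | Survivors with no log score |
|---|---|
| 1% | 8 |
| 5% | 41 |
| 10% | 82 |

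These counts are upper figures for each share, because EQ-5D is analysed only in survivors who consent to active follow-up and provide data (SAP 3.7, population 5).

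**4. What the estimate can do.** All inputs here are assumed, for illustration. Most survivors in both arms score 0.75. The worse arm has 5 percentage points more survivors at a low value v. Mean difference, worse minus better, is 0.05 x (v - 0.75).

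| Low value v | Mean difference | Geometric mean ratio, worse/better |
|---|---|---|
| -0.20 (10% v 5% of survivors) | 0.05 x (-0.95) = -0.0475 | 1.00 after dropping the undefined scores |
| +0.01 (5% v none) | 0.05 x (-0.74) = -0.037 | exp(0.05 x ln(0.01/0.75)) = 0.81 |
| +0.10 (5% v none) | 0.05 x (-0.65) = -0.0325 | exp(0.05 x ln(0.10/0.75)) = 0.90 |

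The largest mean difference goes with no ratio effect at all, and a smaller one with a ratio of 0.81.

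**5. Adding a constant.** For v = -0.20 (10% v 5%), adding c before taking logs gives a ratio of exp(0.05 x ln((c - 0.20)/(c + 0.75))):

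- c = 0.6: exp(0.05 x ln(0.40/1.35)) = 0.941
- c = 0.7: exp(0.05 x ln(0.50/1.45)) = 0.948
- c = 1.0: exp(0.05 x ln(0.80/1.75)) = 0.962

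The answer moves with a constant that the plan does not name.

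**6. Untransformed scale.** A difference in means is defined over the whole range -0.59 to 1.00 and loses no survivor.

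**The case against.** The strongest reply is that the log-linear part is optional. The text says only that the two-part approach will also be considered, and the longitudinal paragraph already provides an untransformed linear mixed model. That is right, and a reader who inferred that EQ-5D can be compared only on the log scale would go beyond the SAP. What remains is T8, which offers no other estimate. SAP 1.4 treats the skeleton tables as a guide but still requires content consistent with Appendix A, so text and table need reconciling.

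Three stronger readings are not supported:

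- **Low-scoring survivors would be counted as dead, because the dead are scored zero.** Part (a) is worded as death versus survival and part (b) is conditional on survival, not on a positive score. Nothing in the SAP reclassifies a living patient.
- **A quality-of-life difference would go unseen.** T8 also gives median and IQR by arm at each time point, Appendix B shows every EQ-5D dimension down to its worst level, and T6 shows mRS 0 to 6. Only the model estimate is at risk.
- **The economic results are affected.** The SAP excludes the economic evaluation, which has its own methods in Protocol 6.5.

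The general clause in SAP 6.2.4 leaves room to change method, so deletion of these patients is a likely consequence and not something the SAP states. But the clause fixes nothing in advance. A generalised linear model with a log link could keep some non-positive scores, but it yields a ratio of arithmetic means, not the geometric mean ratio in T8.

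**Conclusion.** The point holds in this limited form. The log-linear survivor part and the T8 entry are incompatible with the index range in SAP 5.3, and T8 does not match the linear mixed model named in 6.2.2. The mathematical conflict needs no assumption. Its practical size does: 8 to 82 patients rests on an assumed share of 1% to 10%, and the ratios above rest on assumed scores and an assumed imbalance between arms. For the VAS the problem is confined to survivors at exactly 0. Only secondary outcomes 10 and 13 are involved, and SAP 6.2.2 keeps them out of the primary outcome paper. The primary outcome and sample size are unaffected. This should be fixed before EQ-5D is compared between arms, but it is not critical to the trial.

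**What to change.** 1. In SAP 6.2.2, keep the logistic part on death versus survival as written.
2. Replace the log-linear part by a linear (mixed) model on the untransformed index and VAS among survivors, in line with the longitudinal paragraph. Use robust or bootstrap standard errors that allow for clustering by paramedic.
3. State that the survivors-only fallback uses the same untransformed scale.
4. In T8, change the overall entry for index and VAS from OR, GMR to OR, mean difference (95% CI).

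The cost is a SAP amendment, one table cell per score and a change in analysis code, with no new data. There is a small downside: untransformed utilities remain skewed with a ceiling at 1, which is why robust or bootstrap errors are needed.
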